### **Purpose of the Study:**

This is a prospective, randomized vanguard trial of trauma patients admitted to the trauma surgery service at IMC who are deemed to be at high risk for venous thromboembolism (VTE). Once identified and enrolled, subjects will be randomized to receive bilateral lower extremity duplex ultrasound (DUS) surveillance (see Appendix A) versus no surveillance. We will compare the two groups with regard to deep vein thrombosis (DVT) and pulmonary embolism (PE) rates, both during the index hospitalization and at 90 days post-discharge. To our knowledge, this is the first prospective, randomized study of its kind to occur since the widespread use of low molecular weight heparins (LMWH) for VTE chemoprophylaxis in trauma patients. The results of this trial will help to assess the feasibility of performing a definitive (likely multi-institutional) trial in the

future.

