### **Hypothesis/Research Questions:**

This study will determine the rate of VTE (DVT and PE) in high-risk trauma patients who have surveillance for lower extremity DVT versus those who do not have surveillance. It will also determine the rate of DVT propagation to the popliteal vein or higher by 14 days after discharge in high-risk trauma patients found to have isolated distal DVT.

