**Data Analysis/Statistics:**

A historic baseline incidence of the composite outcome of major bleeding events plus proximal DVT on the trauma service is about 5.5%. We expect that in the no surveillance group, the incidence of the composite outcome will be higher. We are not entirely sure how much higher, which is one of the reasons for performing this vanguard trial. The below power analysis reflects that. Based on this power analysis, we would need to enroll at least 1000 subjects in each arm to discern a true difference, perhaps more, depending on the difference in events between the two groups. It is unreasonable given current financial and time constraints to do this definitively at a single center.

Based on historical trauma service admissions of 3000 per year, we estimate that 65-75% of admitted patients will qualify for the study, and 50-75% of those will agree to enroll. Thus, we estimate that over the course of one year, we could enroll about 300 patients per arm. This number of patients should be sufficient to help us determine the feasibility of a definitive, likely multi-institutional future trial.

A chi-squared test will be calculated to compare the rate of VTE between the surveillance group and the no surveillance group

Effect Size	Minimum Sample Size per Group
6.5% (+1.0%)	Doesn't achieve 80% power at n=5000 per group
7.0% (+1.5%)	4,200
7.5% (+2.0%)	2,500
8.0% (+2.5%)	1,600
8.5% (+3.0%)	1,200
9.0% (+3.5%)	900
9.5% (+4.0%)	700
10.0% (+4.5%)	600

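### The power table rests on major bleeding plus proximal DVT, which has no specified analysis, while the one named between-arm test, on unrestricted VTE, would largely compare detection

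*Combined protocol and SAP*

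**What the plan says.** Data Analysis/Statistics sets out the sizing on a composite: "A historic baseline incidence of the composite outcome of major bleeding events plus proximal DVT on the trauma service is about 5.5" per cent. It continues: "We expect that in the no surveillance group, the incidence of the composite outcome will be higher", and then: "We are not entirely sure how much higher, which is one of the reasons for performing this vanguard trial". The table that follows gives sample sizes for composite rates of 6.5% to 10.0% against that baseline. The planned enrolment of about 300 per arm comes from expected recruitment and is justified as enough to judge the feasibility of a definitive trial.

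The same section names a single between-arm test: "A chi-squared test will be calculated to compare the rate of VTE between the surveillance group and the no surveillance group". This agrees with Purpose of the Study ("We will compare the two groups with regard to deep vein thrombosis (DVT) and pulmonary embolism (PE) rates") and with Hypothesis/Research Questions ("This study will determine the rate of VTE (DVT and PE) in high-risk trauma patients"). Neither limits VTE to symptomatic or proximal events.

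Three other places bear on the point:

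- The hypothesis at the end of Background and Significance concerns symptomatic DVT, DVT propagation, and symptomatic or fatal PE.
- Methods/Procedures schedules ultrasound on days 1, 3, 7 and weekly in the surveillance arm, and only for symptoms in the other arm. It closes with a general commitment to compare outcome variables between the groups.
- Data Collection records asymptomatic DVT for the surveillance group only (item 9), symptomatic DVT/PE for all subjects (item 10), propagation (item 11) and bleeding (item 12).

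**The concern.** There are two linked problems.

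First, the endpoint that is sized is not the endpoint that is tested. VTE leaves out bleeding and takes in distal DVT and PE. The plan says the vanguard should help show how far the composite differs without surveillance, but specifies no test, estimate or interval for it.

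Second, the tested endpoint is ascertained unequally. The Significance section says about 85% of the DVTs diagnosed on the service are silent, that the DVT rate would fall if surveillance of the highest-risk patients stopped, and that better outcomes would not necessarily follow. A VTE comparison that counts silent clots therefore counts, in one arm only, events that the other arm is not examined for. Blinded adjudication does not repair this, because adjudicators can judge only events that someone looked for.

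At stake is the decision on a definitive trial. The one named test could show significantly more VTE with surveillance through detection alone, while the composite difference needed to size that trial goes unreported.

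**Working it through.** **1. The plan's own table.** Inputs: baseline 5.5%, 80% power (both from Data Analysis/Statistics), two-sided 5% (assumed; alpha is not stated), equal arms. The formula per arm is n = [1.96·√(2p̄(1−p̄)) + 0.842·√(p1(1−p1)+p2(1−p2))]² / (p2−p1)², where p̄ is the mean of the two rates.

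| No-surveillance rate | Plan | Pooled | Continuity-corrected |
|---|---|---|---|
| 6.5% | not reached at 5,000 | 8,853 | 9,052 |
| 7.0% | 4,200 | 4,087 | 4,220 |
| 7.5% | 2,500 | 2,384 | 2,483 |
| 8.0% | 1,600 | 1,580 | 1,659 |
| 8.5% | 1,200 | 1,135 | 1,201 |
| 9.0% | 900 | 861 | 917 |
| 9.5% | 700 | 680 | 729 |
| 10.0% | 600 | 554 | 597 |

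Every stated row is within 3% of one of the two versions. The table is sound for the composite.

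**2. What the named test would do through detection alone.** Inputs from Significance: DVT rate about 3%, of which about 85% silent. Assume these apply to the arms, that true clots are equal, that scanning finds all silent clots, and that none is found without it.

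- Surveillance: 3%, or 0.03 × 300 = 9 expected cases.
- No surveillance: 0.15 × 3% = 0.45%, or 0.0045 × 300 = 1.35 expected cases.

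The probability of a significant result is the sum, over two independent binomials with n = 300, of all outcomes that the chi-squared test rejects at two-sided 5%. Direction: more VTE with surveillance.

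| Scenario | Surveillance vs none | Probability (Yates) |
|---|---|---|
| DVT only | 3% vs 0.45% | 0.71 (0.59) |
| Add 0.5 point PE to both arms (assumed) | 3.5% vs 0.95% | 0.59 (0.47) |
| Add 1 point PE to both arms (assumed) | 4% vs 1.45% | 0.50 (0.39) |
| DVT only, 25% of silent clots later present in controls | 3% vs 1.09% | 0.39 (0.27) |
| DVT only, 50% later present | 3% vs 1.73% | 0.18 (0.11) |
| DVT only, scanned arm at 5.5% | 5.5% vs 0.83% | 0.95 (0.91) |

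The late-presentation rows use 0.45% + f × 2.55%, with f = 0.25 or 0.50. For comparison, a sound test with no true difference would reject in this direction about 2.5% of the time.

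**3. Precision for the composite at 300 per arm.** Half-width = 1.96·√[(p1(1−p1)+p2(1−p2))/300]. This gives 3.6 points at 5.5% vs 5.5%, 4.1 at 5.5% vs 8.5%, and 4.3 at 5.5% vs 10%.

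**4. Power for a symptomatic endpoint at 300 per arm.** Take 0.45% symptomatic DVT plus an assumed 0, 0.5 or 1 point of PE, doubled without surveillance. Exact power of the uncorrected test is about 8% (0.45% vs 0.90%), 15% (0.95% vs 1.90%) and 23% (1.45% vs 2.90%). With Yates correction it is 2%, 8% and 15%.

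**The case against.** The strongest defence is that the VTE test matches the stated purpose and research question, that feasibility is the main aim, and that Methods/Procedures already commits to comparing outcome variables to investigate the hypothesis, which is framed in symptomatic terms. All of that is true. Bleeding and DVT location are also collected, so the composite can be computed. What remains is that the general commitment names no method and no priority, and the one test that is named carries no restriction to symptomatic events.

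A second objection is that the illustration's inputs do not describe the trial arms. This also stands. The 3% is a service-wide rate under partial scanning: Background and Significance says only high-risk patients who cannot receive enoxaparin are now scanned on a schedule. A fully scanned high-risk arm could well have a higher rate, and late presentation in controls or the inclusion of PE would lower the probabilities. They show the mechanism and a range, and are not predictions.

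A reader might infer that the composite would fall without surveillance, so that the plan's expected direction contradicts its own figures. The documents do not support this. Proximal DVT is open to the same detection effect, but no split of the 5.5% into bleeding and DVT is given, nor is it said whether silent proximal DVT counts. The direction is an unexamined assumption and not an error.

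A reader might also fault the target in "Based on this power analysis, we would need to enroll at least 1000 subjects in each arm to discern a true difference" for not stating its assumed difference. The table brackets it (1,200 at +3.0 points, 900 at +3.5) and the text adds "perhaps more, depending on the difference in events between the two groups", so nothing turns on it.

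**Conclusion.** The point holds on the text. The sized composite has no specified analysis, and the one named test is on an endpoint that matches the stated purpose but neither the sizing nor the symptomatic hypothesis. As written, that test would largely compare detection.

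Under the stated assumptions the chance of a significant result against surveillance with no true difference in clots runs from 0.18 to 0.95, with 0.71 for the plan's own 3% and 85% (DVT only) and 0.50 to 0.59 once an assumed PE rate is included. These figures rest on equal true clot rates, complete detection by scanning, a two-sided 5% level, and the transfer of service-wide rates to the arms.

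It would go too far to say that learning the composite difference is the purpose of the vanguard; the plan calls it one of the reasons. It would also go too far to say that the sample size is wrong. The table reproduces, and the 300 per arm rests on recruitment. This should be fixed before analysis, but it does not call the design into question.

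**What to change.** In Data Analysis/Statistics:

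1. Replace the unrestricted VTE comparison with the between-arm difference and 95% confidence interval for symptomatic DVT plus symptomatic or fatal PE. Any test should be secondary.
2. Report screen-detected silent DVT, DVT propagation and major bleeding separately. Propagation belongs to the hypothesis and should be kept, with a note that it too is affected by unequal scanning.
3. Specify the composite difference with a 95% confidence interval, overall and by component, separating symptomatic from screen-detected proximal DVT, so that it can inform the size of the definitive trial.

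The cost is wording and analysis only. Data Collection items 9 to 12 already capture the components, and enrolment does not change.

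The downsides should be stated. Symptomatic events will be few, with only about 8% to 23% power at 300 per arm for an assumed doubling, which is why estimation should lead. The composite difference will be known only to about ±3.6 to ±4.3 points. Symptom-driven imaging is still ordered by clinicians who know the allocation, so the change reduces unequal ascertainment without removing it.

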**Data Collection:**

[figure not shown]
The following variables will be collected for all subjects in both arms of the study in a secure, computerized database (REDcap):

1. Patient demographics
2. Past medical/surgical/family/social history
3. Mechanism of injury
4. Injuries sustained and Injury Severity Score (ISS)
5. All items in the Caprini DVT risk assessment model (See Appendix C)—this information will be used for descriptive purposes and as a means of comparing the two study groups.
6. All items in the Risk Assessment Profile (RAP) for VTE (See Appendix D)—this information will be used for descriptive purposes and as a means of comparing the two study groups.
7. VTE pharmacoprophylaxis agent, dose, time from admission to first dose, interruptions in pharmacoprophylaxis and for what reason
8. Mechanical prophylaxis modality used
9. Asymptomatic DVT in surveillance group with location
10. Symptomatic DVT/PE with location during hospitalization and at 90 days
11. DVT propagation with location during hospitalization and at 14 days
12. Major and clinically relevant bleeding during hospitalization and at 90 days (see Appendix E).
13. All cause mortality during hospitalization and at 90 days

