##### Each Risk Factor Represents 2 Points

- Age 60-74 years
- Arthroscopic surgery
- Malignancy (present or previous)
- Major surgery (> 45 minutes)
- Laparoscopic surgery (> 45 minutes)
- Patient confined to bed (> 72 hours)
- Immobilizing plaster cast (< 1 month)
- Central venous access

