#### **Appendix D: Risk Assessment Profile (RAP)**

Variable	Points
Underlying Condition	
Obesity	2
Malignancy	2
Abnormal Coagulation	2
History of Thromboembolism	3
Iatrogenic Factors	
Femoral Central Line >24 hrs	2
Transfusion, >4 units in 24 hrs	2
Surgery lasting >2 hrs	2
Repair or ligation of major vascular injury	3
Injury-related Factors	
Chest AIS > 2	2
Abdomen AIS >2	2
Head AIS > 2	2
Spinal Fracture	3
GCS <8 for >4 hrs	3
Complex lower extremity fracture	4
Pelvis fracture	4
Spinal Cord injury, paraplegia or quadriplegia	4
Age (yrs)	
≥40 but <60	2
≥60 but <75	3
≥75	4

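### The one stated outcome test leaves baseline risk data unused (a small loss of precision), and the risk scores need a pre-randomization cut-off before they can serve as baseline values

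*Combined protocol and SAP*

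**What the plan says.** All references are to the combined protocol and SAP.

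- **Data Analysis/Statistics** names one test: "A chi-squared test will be calculated to compare the rate of VTE between the surveillance group and the no surveillance group". It gives no covariate, effect estimate or confidence interval. The event rates there belong to another outcome: "A historic baseline incidence of the composite outcome of major bleeding events plus proximal DVT on the trauma service is about 5.5" per cent.
- **Data Collection**, items 5 and 6, records every item of the Appendix C score and of the RAP in both arms. The stated use is: "this information will be used for descriptive purposes and as a means of comparing the two study groups". No time point for scoring is given.
- **Methods/Procedures** has subjects enrolled within 24 hours of admission and then randomized. **Randomization** names no stratification factor.
- **Appendix D** (RAP) includes "Femoral Central Line >24 hrs", surgery over 2 hours and transfusion of more than 4 units in 24 hours. **Appendix C** includes "Patient confined to bed (> 72 hours").
- **Appendix A** admits a subject on any single factor, from age over 40 to spinal cord injury.

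**The concern.** Two separate things are at stake.

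**Unused precision.** Entry on any one factor makes baseline risk heterogeneous. The data that describe this risk are collected on everyone, yet the outcome analysis does not draw on them. The plan says that one reason for the vanguard trial is uncertainty about the size of the difference between arms. A p-value does not answer that; an estimate with an interval does, and adjustment can narrow the interval somewhat.

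**Scores that are not baseline values.** The plan intends to use the risk items to compare the arms. Some items can first be met after allocation. Clinicians know the arm, since only the outcome adjudicators are blinded. Surveillance starts on post-injury day 1, and a proximal DVT that it finds leads to anticoagulation, so a later item such as transfusion could itself depend on arm. A difference in full scores could then be a consequence of allocation that is read as baseline imbalance, or could hide a real one. If a full score were later put into a model, the effect estimate would be exposed to bias.

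**Working it through.** **1. The plan's own sample size.** Inputs from Data Analysis/Statistics: 5.5% versus 8.5%, 80% power, 1,200 per group. Assumed, because not stated: two-sided alpha 0.05 and 1:1 allocation.

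n = [1.96·√(2·p̄·q̄) + 0.8416·√(p₁q₁ + p₂q₂)]² / (p₂ − p₁)², with p̄ = 0.07

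= [1.96·√0.1302 + 0.8416·√0.12975]² / 0.03² ≈ 1,135 per group, or 1,201 with continuity correction. The stated 1,200 is reproduced. Each row from 7.0% to 10.0% lies within 3% of one of these two formulas.

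**2. Precision at 300 per arm, unadjusted.** Expected events are 300 × 0.055 = 16.5 and 300 × 0.085 = 25.5, about 42 in all. The 95% CI half-width is 1.96·√(0.12975/300) = 4.08 points. Power is 30.1%.

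**3. Gain from one baseline covariate at these rates.** The documents give no prognostic strength, so a range is assumed. If the covariate explains R² of the binary outcome, variance and required N scale by about (1 − R²), and the half-width by √(1 − R²).

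| Assumed c-statistic | R² | 1,200 becomes | Power at 300 per arm | Half-width (points) | Simulated variance ratio, arms differing |
|---|---|---|---|---|---|
| 0.64 | 1.4% | 1,183 | 30.5% | 4.05 | 0.99 |
| 0.71 | 3.8% | 1,154 | 31.1% | 4.00 | 0.96–0.97 |
| 0.75 | 6.2% | 1,126 | 31.8% | 3.95 | 0.92–0.93 |
| 0.81 | 10.7% | 1,071 | 33.1% | 3.85 | 0.87–0.90 |

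The last column compares a standardized risk difference from a logistic model with the raw difference (5.5% versus 8.5% or 10%). Across all simulations at these rates, the ratio ran from about 0.85 to 0.99.

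**4. The same at VTE rates.** The test is on VTE, and the rates above are not VTE rates. The only DVT rate given for the service is about 3%, with about 85% of diagnosed DVTs silent (Significance). It is service-wide and excludes PE, so it serves only to mark a lower range. It gives 300 × 0.03 = 9 events per arm. Simulated variance ratios were about 0.91 to 1.00 at rates of 3% or lower.

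An arm without events becomes a practical risk:
- At a true rate of 1%: 0.99³⁰⁰ = 0.049, about 5% of trials.
- At 0.45%, that is 3% × 0.15 if only symptomatic DVTs were found without surveillance: 0.9955³⁰⁰ = 0.258, about 26% of trials.

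An ordinary logistic model fails in those trials.

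**5. Timing of the items.** Subjects are admitted within 24 hours of injury and enrolled within 24 hours of admission, so enrolment falls at most 24 + 24 = 48 hours after injury.

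| Item | Known at enrolment? |
|---|---|
| Bed confinement over 72 h | Not from the injury: 48 < 72 |
| Femoral line over 24 h | Not for a line placed after admission |
| Surgery over 2 h; more than 4 units in 24 h | Sometimes; can also accrue later |
| Age, obesity, history, fractures, spinal cord injury, AIS | Fixed at or before injury, even if coded later |

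**6. Chance imbalance.** For a factor with an assumed prevalence of 30%, the 95% range of the difference between arms is 1.96·√(2 × 0.3 × 0.7/300) = 7.3 points.

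**The case against.** A reader might infer that post-randomization items contaminate the outcome comparison. The documents do not support this. The chi-squared test uses neither score, and in subjects analysed as randomized it is a valid test. Its error rate already allows for chance imbalance such as the 7.3 points above, and no stratification factor is named that would call for adjustment.

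A reader might also infer that a logistic model should replace the test. Step 4 speaks against that: on the outcome actually tested, such a model could fail where a simple comparison still gives an answer.

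Further points on the other side:

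- Data Collection speaks of items, not totals, so a comparison of total scores is an inference (the Appendix C form has a total line, and the RAP lists points). Age, injuries and ISS are recorded separately and can show baseline balance. This stands, and it makes the timing point a matter of clarification.
- No feasibility conclusion changes. This also stands: at 5.5% versus 8.5% the power gain is at most 3 points.
- Adjustment is not wholly free. A date cut on each item would need onset times that are not listed. This stands as far as date cuts go, but leaving out the late-accruing items avoids the need.

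What remains is that baseline items already collected go unused in the outcome analysis, no effect estimate or interval is planned, and no scoring cut-off is stated.

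**Conclusion.** The point holds as a modest improvement to a valid analysis. Adjustment for one baseline score would lower the variance of the risk difference by roughly 1 to 15% at event rates of 5.5 to 10%, and by 0 to 9% at VTE rates near 3% or lower. These figures assume a c-statistic of about 0.64 to 0.81. The higher rates are borrowed from the composite of major bleeding plus proximal DVT. The Background says that the RAP has been validated retrospectively in trauma patients but gives no measure of discrimination.

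The timing problem is confined to the descriptive comparison of arms on the risk scores and to any model that uses a full score.

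It would also go too far to infer that adjustment makes the VTE comparison fair. Asymptomatic DVT is looked for systematically only in the surveillance arm, and a covariate cannot repair unequal detection.

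**What to change.** 1. Keep the chi-squared test as stated.
2. Pre-specify beside it a risk difference with 95% CI, adjusted for one covariate: a RAP score built only from items fixed at or before randomization (for example age, obesity, history, fractures, spinal cord injury and AIS). Leave out femoral line duration, surgery duration and transfusion.
3. Use a method that still works when an arm has few or no events, such as a linear model with robust standard errors, or a penalized logistic model with standardization. Name one in advance.
4. Use the same pre-randomization score for the baseline comparison. If full RAP or Appendix C scores are also shown, label them as including in-hospital events.
5. Do not add enoxaparin contraindication as a covariate. It is not a listed variable; item 7 of Data Collection records only agent, dose, time to first dose, and interruptions with reasons.

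The cost is a little extra analysis and a written scoring rule. Patients, visits and collected fields do not change. The wording should be fixed before outcomes are seen by arm, because a covariate chosen afterwards carries less weight.

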**Funding:**

We have applied for a research grant through the Intermountain Research and Medical Foundation.

## APPENDIX

[figure not shown]
### **Appendix A: Factors that Identify Trauma Patients as High Risk for VTE**

From Intermountain Medical Center Trauma Program Guideline for Venous Thromboembolism, revised 2013.

Any one of these factors identifies a patient as high risk:

1. Pre-Injury Risk Factors
  - a. Obesity (BMI > 30)
  - b. Age > 40 years
  - c. History of VTE
  - d. History of malignancy
  - e. Any known hypercoagulable state
2. Injury-Related Risk Factors
  - a. Major venous injury
  - b. Spinal cord injury
  - c. Spinal fracture
  - d. Major operative procedure of any kind
  - e. Pelvic fracture
  - f. Lower extremity fracture
  - g. Hemorrhagic shock
  - h. Moderate or severe head injury (GCS <13 at presentation)
  - i. ISS > 9
  - j. Central venous line

